14.1 Primary Efficacy Endpoint: Event-free Survival (EFS)

Event-Free Survival (EFS) time is defined as the time (in months) from randomization to the first occurrence of any of the following events as assessed by the BIRC: death due to any cause, disease progression (radiological or clinical), primary treatment failure, relapse (radiological or clinical) or occurrence of a new cancer (see Table 1). Death as reported on the eCRF page "Death" will also be considered in the derivation of EFS time.

$$EFS = (date of EFS event - randomization date +1) / 30.4375$$

Censoring rules for the primary and sensitivity analyses of EFS are described in Table 4 below. The last adequate tumor assessment is defined as the last tumor assessment result that is not "Not evaluable" or "Not assessed". If a participant is meeting a multiple censoring situation, the earliest censoring criterion will be applied.

Table 4: Censoring rules for EFS

Situation	Primary	Sensitivity #1	Sensitivity #2
No evaluable baseline or post-baseline assessment*	Right censored at the date of randomization	Right censored at the date of randomization	Right censored at the date of randomization
Death, PD or any event entering in the definition of EFS after 2 or more consecutive missing or inadequate tumor assessments	Right censored at last adequate assessment before the consecutive missing/inadequate assessments	Right censored at last adequate assessment before the consecutive missing/inadequate assessments	Not applicable
Initiation of a new anticancer treatment for the disease under investigation before any event entering in the definition of EFS	Right censored at their last adequate assessment before the initiation of the new anticancer treatment	Not applicable	Not applicable
No death, PD, nor any event entering in the definition of EFS	Right censored at the date of their last adequate assessment	Right censored at the date of their last adequate assessment	Right censored at the date of their last adequate assessment

Abbreviations: EFS: Event-free survival; PD: Progressive disease

^{*}Any EFS event is considered as a post-baseline assessment.

Table 5: Estimand Attributes EFS

Objective	Estimand Attributes
Primary	
-	Endpoint: EFS as assessed by the BIRC defined as the time from randomization to the first occurrence of any of the following events (occurring within two scheduled tumor assessments after last evaluable assessment or randomization): Death from any cause Progression: Radiological, assessed per RECIST v1.1 or Clinical, with or without RECIST v1.1- radiologically documented progression, assessed endoscopically Primary treatment failure before achieving a CR: requirement for radical salvage surgery that includes the primary tumor site, with documented viable tumor presenting anatomopathological findings even in the absence of formal RECIST v1.1 radiological progression. Any radiological or clinical relapse after achieving a CR (loco-regionally), including any event defined as locoregional treatment failure, even in the absence of formal radiological progressive disease confirmation: Requirement for radical salvage surgery that includes the primary tumor site, regardless of anatomopathological findings or Elective neck dissection or biopsy, with positive viable tumor cells on anatomopathological findings at 22 weeks or later after randomization. Second cancers unless anatomopathological findings exclude squamous histology Population: Patients with LA-SCCHN Stage III, IVA or IVB suitable for definitive CRT Treatment: xevinapant and CRT followed by xevinapant vs placebo and CRT followed by placebo Intercurrent Event Strategy: Death within two missing scheduled tumor assessments after last evaluable assessment or randomization will be considered as event (composite strategy) Discontinuation of treatment: The endpoint will be analyzed regardless of
	 whether or not treatment has been discontinued (treatment-policy strategy) Start of subsequent anticancer therapy will be analyzed according to hypothetical strategy, i.e., tumor assessments after start of subsequent anticancer therapy will not be considered for analysis Population-Level Summary: Hazard Ratio

Objective	Estimand Attributes
Supplementary #1 (CSP Sensitivity #1)	Endpoint: EFS as assessed by the BIRC defined as the time from randomization to the first occurrence of any of the events (occurring within two scheduled tumor assessments after last evaluable assessment or randomization).
	Population: Patients with LA-SCCHN Stage III, IVA or IVB suitable for definitive CRT
	Treatment: xevinapant and CRT followed by xevinapant vs placebo and CRT followed by placebo
	Intercurrent Event Strategy:
	Death within two missing scheduled tumor assessments after last evaluable assessment or randomization will be considered as event (composite strategy)
	 Discontinuation of treatment: The endpoint will be analyzed regardless of whether or not treatment has been discontinued (treatment-policy strategy) Start of subsequent anticancer therapy: The endpoint will be analyzed regardless of the start of subsequent anticancer therapy
	Population-Level Summary: Hazard Ratio
Supplementary #2 (CSP Sensitivity #2)	Endpoint: EFS as assessed by the BIRC defined as the time from randomization to the first occurrence of any of the events.
	Population: Patients with LA-SCCHN Stage III, IVA or IVB suitable for definitive CRT
	Treatment: xevinapant and CRT followed by xevinapant vs placebo and CRT followed by placebo
	Intercurrent Event Strategy:
	 Discontinuation of treatment: The endpoint will be analyzed regardless of whether or not treatment has been discontinued (treatment-policy strategy) Start of subsequent anticancer therapy: The endpoint will be analyzed regardless of the start of subsequent anticancer therapy.
	Population-Level Summary: Hazard Ratio

Objective	Estimand Attributes
Sensitivity #1 (CSP Sensitivity #3)	Endpoint: EFS as assessed by the Investigator defined as the time from randomization to the first occurrence of any of the events (occurring within two scheduled tumor assessments after last evaluable assessment or randomization):
	Population: Patients with LA-SCCHN Stage III, IVA or IVB suitable for definitive CRT
	Treatment: xevinapant and CRT followed by xevinapant vs placebo and CRT followed by placebo
	Intercurrent Event Strategy:
	 Death within two missing scheduled tumor assessments after last evaluable assessment or randomization will be considered as event (composite strategy) Discontinuation of treatment: The endpoint will be analyzed regardless of whether or not treatment has been discontinued (treatment-policy strategy)
	Start of subsequent anticancer therapy will be analyzed according to hypothetical strategy, i.e., tumor assessments after start of subsequent anticancer therapy will not be considered for analysis
	Population-Level Summary: Hazard Ratio

14.1.1 Primary Analysis of the Primary Efficacy Endpoint EFS

The primary efficacy analysis will assess the difference in EFS between treatment arms using a one-sided stratified log-rank test. The significance boundaries are adjusted accordingly to control the family-wise error rate (FWER) at 2.5% one-sided (see also IAP Table 3). The stratification factors are tumor size (T4 vs other) and lymph node involvement (N0-1 vs N2 vs N3). These factors were chosen among the stratification factors for randomization to avoid issues caused by very small sample stratum sizes.

A Cox-proportional hazard regression model adjusted for the randomization factors will be used on the EFS with primary censoring rule (Table 4) to derive the hazard ratio and 95% CI between the 2 randomized regimens. In addition, a two-sided repeated CI (RCI) for the hazard ratio will be reported (Jennison and Turnbull, 2000), to account for the group sequential design in the confirmatory analyses (interim and primary analysis, as applicable). Ties will be handled by replacing the proportional hazards model by the discrete logistic model. The stratification factors used for the randomization of participants will be inserted as covariates in the regression model. EFS with sensitivity censoring rules will be analyzed with the same approach.

A further estimate of the hazard ratio (including 95% confidence interval) will be calculated based on the Cox proportional hazards model stratified by the stratification factors tumor size (T4 vs other) and lymph node involvement (N0-1 vs N2 vs N3). Each stratum will define separate

baseline hazard functions. Ties will be handled by replacing the proportional hazards model by the discrete logistic model.

The null and alternative hypotheses can be described in terms of hazard ratios as:

$$H_0^{EFS}$$
: $\lambda_{(xevinapant + CRT)} / \lambda_{(placebo + CRT)} \ge 1$ versus

$$H_1^{EFS}$$
: $\lambda_{(xevinapant + CRT)} / \lambda_{(placebo + CRT)} < 1$,

where $\lambda_{(xevinapant + CRT)}$, $\lambda_{(placebo + CRT)}$ represents the hazard of EFS for the (xevinapant + CRT) and the (placebo + CRT) group respectively.

The SAS code for the stratified log-rank test and the Cox-proportional hazard regression model is specified in Appendix 6

The proportional hazards assumption for the analysis of EFS will be examined using graphical methods by means of log-log-Survival plots (log(-log(S(t)))) vs log(time) by treatment arm, plots=(lls) in PROC LIFETEST.)

Kaplan-Meier methodology will be used to estimate EFS as assessed by the BIRC (with primary censoring rule as defined in Table 4) in each treatment arm together with a summary of associated statistics: median time with corresponding two-sided 95% CIs, Q1 and Q3, min and max. Event-free rates at 9, 12, 18, 24, 30 and 36 months after randomization will be estimated with corresponding two-sided 95% CIs. Other rates may be displayed. For each interval the number of participants at risk at the start of the interval as well as the number of participants failed during the interval will be reported.

Kaplan-Meier estimates and median time are calculated with the PROC LIFETEST procedure in SAS. CIs for the median and the estimated survival rates at the time points defined above will be derived using the log-log transformation according to Kalbfleisch and Prentice (2002) [CONFTYPE=LOGLOG option (default)] based on standard errors computed using Greenwood's formula.

The SAS code for the Kaplan-Meier estimates is specified in Appendix 6

Graphical representation of the survival curves as step functions will be provided per treatment arm and per stratification variable.

The number and percentage of participants with each event type (death due to any cause, disease progression (radiological or clinical), primary treatment failure, relapse (radiological or clinical) or occurrence of a new cancer) as assessed by the BIRC and censoring reasons will be presented by treatment arm for all 3 censoring scenarios as presented in Table 4.

The EFS time or censoring time and the reasons for censoring will also be listed for all 3 censoring scenarios as presented in Table 4.

A summary of concordance of EFS between BIRC and investigator assessment will be provided including status of "No Event" and which type of EFS event as well as number of cases where EFS was assessed at different timepoints by BIRC and investigator (shift tables per treatment arm).

Follow-up for EFS

In order to assess the follow-up for EFS, Kaplan-Meier estimates will be calculated using the censoring rules with reverse censoring indicator.

14.1.2 Sensitivity Analyses of the Primary Efficacy Endpoint EFS

To assess the robustness of the primary efficacy endpoint the following sensitivity analyses will be performed:

Table 6: Sensitivity analyses for EFS

Sensitivity analysis	Population	Censoring rules (Table 4)	Endpoint	Statistical methods
1	ITT	Primary	EFS as assessed by Investigator	same as primary EFS analysis (Section 14.1.1), incl. Kaplan-Meier curves

Frequency (number and percentage) of participants with each event type (death due to any cause, disease progression (radiological or clinical), primary treatment failure, relapse (radiological or clinical) or occurrence of a new cancer) as assessed by the investigator and censoring reasons will be presented by treatment arm.

The EFS time or censoring time and the reasons for censoring will also be listed.

A further sensitivity analysis to address possible biases due to the dynamic allocation process will be performed based on permutation testing for the primary endpoint EFS by BIRC. To this end, the stratified log-rank test as described in 14.1.1 for the primary endpoint EFS by BIRC will be repeated with rerandomized xevinapant and placebo arms. The rerandomized treatment arms are determined by reapplying the dynamic allocation approach using the actual randomization dates and randomization factors for all participants. The permutation test will be conducted with 10,000 replications.

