event count of the previous interim analysis (about 10% increase in information fraction) but not later than 12 months after the previous interim analysis cut-off date.

A hierarchical testing procedure will be used to test first primary null hypothesis H₀^{EFS} in a group sequential design, which uses alpha-spending according to Lan-DeMets with O'Brian-Fleming-like boundaries planning for a total number of 429 EFS events at primary analysis. If and only if that can be rejected either on interim or primary analysis, the null hypothesis H₀^{OS} will be confirmatory tested in a group sequential design with interim analysis as planned in Table 2, which uses alpha-spending according to Lan-DeMets with O'Brien Fleming-like boundaries planning for a total number of 386 OS events at final analysis. Table 3 shows the operating characteristics and decision boundaries for the confirmatory interim and primary/final analyses as planned.

Table 3: Operating Characteristics and Power Estimations

		Boundaries (HR) Boundaries (P-value)		Local			
Analysis	Events (IF)	Efficacy	Futility	Efficacy	Futility	Power ^a	Power ^a
EFS IA1	279 (65%)	0.737	0.886	0.005	0.163	53.3%	
EFS IA2	365 (85%)	0.793	-	0.013	-	25.8%	_
EFS PA	429 (100%)	0.821	0.821	0.020	0.020	9.1%	88.2%
OS IA1	154 (40%)	0.583	-	0.0004	-	5.7%	
OS IA2	216 (56%)	0.684	-	0.003	-	19.4%	_
OS IA3	270 (70%)	0.739	-	0.007	-	21.1%	
OS IA4	309 (80%)	0.767	-	0.010	-	13.5%	
OS FA	386 (100%)	0.813	0.813	0.021	0.021	19.9%	79.6%

Abbreviations: EFS: event-free survival; **HR**: hazard ratio; **IA**: interim analysis; **IF**: information fraction; **OS**: overall survival; **PA**: primary analysis.

Note: Decisions will be based on p-values with respect to actual number of events. Expected HRs under the assumption of an exponential distribution are only given as further information.

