6.1 Safety Monitoring Analysis

The IDMC will review quarterly descriptive summaries of accumulating participants' disposition and safety. The analyses will be conducted by unblinded supporting staff independent from the study team. The investigators/site personnel, CRO and sponsor team will remain blinded, except for a dedicated unblinded statistical team at the CRO that is preparing analyses for the IDMC.

The primary intent of these analyses is the patient safety monitoring. IDMC may recommend change or early stop of the study in case of safety issue.

Details on outputs used to support the review by the IDMC are available in the IDMC TFL shell document.

^a Power estimations are based on an assumed HR=0.73 for EFS and a HR=0.75 for OS and the prerequisite that the EFS null hypothesis can be rejected at either IA or PA. Futility-bounds are non-binding.

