14.2.1 Overall Survival

Overall Survival (OS) time is defined as the time (in months) from randomization to death due to any cause.

$$OS = (date \ of \ death - randomization \ date +1) / 30.4375$$

Participants without documented death at the time of analysis will be censored at the date of last known contact.

The treatment difference in OS between the 2 treatment arms will be assessed using a one-sided stratified log-rank test as described for the primary analysis of EFS in Section 14.1.1. The significance boundaries are adjusted accordingly to control the family-wise error rate (FWER) at 2.5% one-sided (see also Table 3). The stratification factors are tumor size (T4 vs other) and lymph node involvement (N0-1 vs N2 vs N3).

The null and alternative hypotheses can be described in terms of hazard ratios as:

$$H_0^{OS}$$
: $\lambda_{(xevinapant + CRT)} / \lambda_{(placebo + CRT)} \ge 1$ versus

$$H_1^{OS}$$
: $\lambda_{(xevinapant + CRT)} / \lambda_{(placebo + CRT)} < 1$,

where $\lambda_{(xevinapant + CRT)}$, $\lambda_{(placebo + CRT)}$ represents the hazard of OS for the (xevinapant + CRT) and the (placebo + CRT) group respectively.

The treatment effect will be analyzed using a Cox Proportional Hazard model as described for the primary analysis of EFS in Section 14.1.1 including the RCI for the hazard ratio.

A further sensitivity analysis to address possible biases due to the dynamic allocation process will be performed based on permutation testing for the secondary endpoint OS as described for the primary endpoint EFS by BIRC in Section 14.1.2.

The Kaplan-Meier method (as described for the primary analysis of EFS in Section 14.1.1) will be used to estimate the OS in each treatment arm. Survival rates at 12, 24, 36, 48, and 60 months after randomization will be estimated with corresponding two-sided 95% CIs.

Graphical representation of the survival curves (Kaplan-Meier estimates) as step functions will be provided per treatment arm and per stratification variable.

The number and percentage of deaths will be presented by treatment arm. The OS time or censoring time will also be listed.

The same subgroup analyses as described for the EFS in Section 14.1.4 will be performed for OS.

Table 8: Estimand Attributes OS

Objective	Estimand Attributes
Secondary	
To demonstrate improvement in	Endpoint: OS defined as the time from date of randomization to death

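### With 10,000 replications, the re-randomization check on OS is too imprecise to settle a borderline result at the first OS interim analysis, where the planned boundary is 0.0004

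*SAP*

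**What the plan says.** SAP Section 14.1.2 repeats the stratified log-rank test for EFS after treatment arms have been reassigned by rerunning the dynamic allocation on the actual randomization dates and factors. It fixes the count: "The permutation test will be conducted with 10,000 replications".

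For OS, Section 14.2.1 states the purpose, "A further sensitivity analysis to address possible biases due to the dynamic allocation process will be performed", and the method, "based on permutation testing for the secondary endpoint OS as described for the primary endpoint EFS by BIRC in Section 14.1.2". No separate count is given, so 10,000 carries over.

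OS is tested with a design that "uses alpha-spending according to Lan-DeMets with O'Brien Fleming-like boundaries planning for a total number of 386 OS events at final analysis", within an overall error rate of 2.5% one-sided. The first OS row of SAP Table 3 reads "OS IA1 154 (40%) 0.583 - 0.0004 - 5.7": 154 events, hazard ratio boundary 0.583, p-value boundary 0.0004 and 5.7% power at that look. The later OS boundaries are 0.003, 0.007, 0.010 and 0.021. The EFS boundaries are 0.005, 0.013 and 0.020.

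The SAP does not say how the re-randomization p-value is to be estimated, whether its Monte Carlo uncertainty will be reported, or at which OS looks the test will be run.

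**The concern.** A re-randomization p-value is a proportion estimated by simulation, so its precision depends on how many replicates are at least as extreme as the observed statistic. A count that suits p-values around 0.005 to 0.020 may be too small for one around 0.0004.

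This is the only analysis that the SAP labels as addressing bias from the dynamic allocation, and OS is the only secondary endpoint tested confirmatorily. If OS crosses at IA1, readers will naturally set the re-randomization p-value beside the boundary that the log-rank p-value had to meet. For a near-boundary result, agreement or disagreement could then come from simulation noise and not from the allocation.

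**Working it through.** **Inputs.** R = 10,000 replicates (SAP 14.1.2, carried to OS by 14.2.1). OS looks at 154, 216, 270, 309 and 386 events, with the boundaries above (SAP Table 3). One-sided alpha 0.025. Assumed OS hazard ratio 0.75 (Table 3 footnote).

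**1. Reproducing the plan's boundary.** The Lan-DeMets O'Brien-Fleming-type function spends 2 × [1 − Φ(z(1 − α/2)/√t)]. At t = 154/386 = 0.399, with z(0.9875) = 2.2414, this is 2 × [1 − Φ(2.2414/0.6316)] = 2 × [1 − Φ(3.549)] = 0.00039, which is z = 3.362. The hazard ratio boundary is exp(−2 × 3.362/√154) = 0.582. Power at this look under HR 0.75 is 5.7%. The later OS p-value boundaries also agree with Table 3 to the precision printed, so 0.0004 is sound.

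**2. Precision at each boundary.** If the true re-randomization p equals the boundary, the expected number of exceedances is R × p and the Monte Carlo SE is √(p(1 − p)/R).

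| Look | p | Expected exceedances | SE | Relative SE |
|---|---|---|---|---|
| OS IA1 | 0.0004 | 4 | 0.00020 | 50% |
| OS IA2 | 0.003 | 30 | 0.00055 | 18% |
| OS IA3 | 0.007 | 70 | 0.00083 | 12% |
| OS IA4 | 0.010 | 100 | 0.00099 | 10% |
| OS FA | 0.021 | 210 | 0.00143 | 7% |
| EFS IA1 | 0.005 | 50 | 0.00071 | 14% |
| EFS IA2 | 0.013 | 130 | 0.00113 | 9% |
| EFS PA | 0.020 | 200 | 0.00140 | 7% |

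If 4 exceedances are seen, the exact 95% interval for p is 0.00011 to 0.00102.

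**3. Borderline results at OS IA1.** Let b be the number of exceedances. The estimate b/R is at or below 0.0004 when b ≤ 4. The estimate (b + 1)/(R + 1) is at or below 0.0004 when b ≤ 3. From the binomial distribution with R = 10,000:

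- True p = 0.0003, a genuine crossing: the estimate is above 0.0004 in 18% of runs (b/R) or 35% ((b + 1)/(R + 1)).
- True p = 0.0006, not a crossing: the estimate is at or below 0.0004 in 28% or 15% of runs.

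With 100,000 replicates the corresponding figures are 3% and 5%, then under 1% for both. The estimator matters at this resolution: four exceedances give 0.0004 by one formula and 0.0005 by the other.

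**4. Clear crossings at OS IA1.** With b = 0 the exact upper limit for p is 0.00030 (one-sided 95%) or 0.00037 (two-sided 95%), both below 0.0004. With b = 1 the limits are 0.00047 and 0.00056, both above it. Treating the log-rank and re-randomization p-values as equal, the median p among IA1 crossings under HR 0.75 is about 0.00012. The (b + 1)/(R + 1) estimate is then at or below 0.0004 in about 87% of crossings, and b = 0 occurs in about 40%.

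**5. More replicates at p = 0.0004.** With 100,000, 40 exceedances are expected (SE 0.000063, 16% relative; 95% interval 0.00029 to 0.00054 if 40 are seen). A 10% relative SE needs (1 − 0.0004)/(0.0004 × 0.01) = 249,900, about 250,000. With 1,000,000, 400 are expected (SE 0.00002, 5% relative).

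**6. A moving boundary.** SAP Section 6.2 recalculates the OS boundary from the deaths actually observed, and the combined first look is triggered by EFS events. If, as an assumption, only 130 to 140 deaths had occurred, the same spending function gives 0.00011 to 0.00020, and 10,000 replicates would be thinner still.

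**The case against.** The strongest reply is that nothing in the SAP ties this test to the boundary. Confirmatory decisions rest on the stratified log-rank test against boundaries recalculated from observed events; the re-randomization test is a sensitivity analysis. A reader can judge whether an estimate of 0.0002 or 0.0006 broadly supports the log-rank result, and more replicates could be run if the case arose. This stands, and it makes the matter one of precision and not of validity.

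The affected case is also uncommon. OS IA1 is tested only if the EFS null hypothesis has been rejected, power at that look is 5.7%, and only near-boundary results within it are in doubt. That stands too.

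Two stronger readings are tempting. A reader might infer from the 4 expected exceedances that the check cannot confirm an OS IA1 claim. That does not follow: four is the expectation only when the true p sits at the boundary, and a clearer crossing gives fewer, with zero putting the upper limit below 0.0004. A reader might also infer that the Monte Carlo error is as large as the quantity checked at both early OS looks. It is half of it at IA1 and 18% at IA2.

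Nor is this test the plan's only protection. The Cox models for EFS and OS adjust for all four randomization factors, and the allocation in protocol Section 6.3 has random elements built in. It is the only analysis labelled for the purpose. What remains is that the count was set for EFS and carried over to a look where it is thin, with the estimator left open.

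**Conclusion.** The point holds in a limited form and is minor. At a true re-randomization p near 0.0004, 10,000 replicates give a 50% relative Monte Carlo error, too imprecise to settle a borderline OS IA1 result. A genuine crossing at p = 0.0003 would be estimated above 0.0004 in about 18% to 35% of runs, depending on the estimator.

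It does not extend to clear crossings at IA1, to EFS or to the later OS looks; OS IA2 is affected only mildly. It has no bearing on type I error or on the confirmatory OS decision.

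The error rates assume that a reader compares the estimate with the planned 0.0004, which the SAP does not require. The 87% agreement figure also assumes that the log-rank and re-randomization p-values coincide, with a true hazard ratio of 0.75.

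**What to change.** In SAP Section 14.2.1, give the OS re-randomization test its own specification:

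- Set at least 100,000 replicates at OS IA1; about 250,000 if a 10% relative SE at 0.0004 is wanted.
- Name the p-value estimator, for example (b + 1)/(R + 1).
- Report the Monte Carlo confidence interval with the p-value.

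Keep 10,000 for EFS. This takes a sentence or two in the SAP and computer time. Design, alpha allocation and data collection are unchanged. The count is best fixed before unblinding, so that a later increase does not look prompted by the result.
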